4.7.6 Anti-drug Antibodies

For patients under treatment, there is a potential for them to develop anti-drug antibodies (ADA) over time. The plasma sampling for anti-drug antibody assessment data will be available for baseline and pre-dose at each time point post-baseline and follow-up visit 6

months after the last dose (or early termination visit). Data will be presented in summary tables (proportions of baseline prevalence and incidence of ADA by dose level and a listing of patients who tested positive for ADA).

The following definitions based on [3] as well as a Sponsor's definition for ADA with neutralizing potential will be used to describe patients' immunogenicity:

- ADA Positive
 - Treatment induced: ADA developed de novo (seroconversion) following drug administration. Patients who have no pre-existing ADA or are missing ADA data before drug administration and who have at least one ADA positive sample following drug administration.
 - Treatment boosted: Patients who have pre-existing ADA and have a ≥ 4 fold increase in ADA titer following drug administration compared to baseline measurement.
- ADA Negative
 - ADA negative all samples: Patients who have no pre-existing ADA (i.e. antibodies reactive with the drug that are present in patients before treatment) or are missing ADA data before drug administration and who have all negative ADA results following drug administration, and treatment unaffected ADA-negative patients.
 - Treatment unaffected ADA: Patients who had positive sample at baseline and post-baseline were either negative or positive but do not have a ≥ 4 fold increase in ADA titer following drug administration compared to baseline measurement.
- Transient ADA
 - Treatment-induced ADA detected only at one sampling time point during the treatment or follow-up observation period (excluding the last sampling time point).
- Persistent ADA
 - Treatment-induced ADA detected at 2 or more sampling time points during the treatment or follow-up observation period, or detected on last sampling time point.

4.7.7 Physical/Neurological Examination

A complete physical and neurological examination will be performed at screening and at other visits as specified in the schedule of activities (refer to the study protocol Appendices 1 and 2 for details). Unlike other assessments which will be pre-dose, neurological examination will be pre and post dose on each dosing day.

Any abnormality identified at baseline will be recorded on the General Medical History and Baseline Conditions eCRF. Changes from baseline abnormalities will be recorded in patient notes. New or worsened clinically significant abnormalities (i.e., beyond expected variation or normal age-related change) will be recorded as adverse events on the Adverse Event eCRF.

Respective assessments will be summarized in their respective eCRF aforementioned category.

4.7.8 Columbia-Suicide Severity Rating Scale

The Columbia-Suicide Severity Rating Scale (C-SSRS) is a structured tool to assess suicidal ideation and behavior. Four constructs will be assessed: severity of ideation, intensity of ideation, behavior and lethality of actual suicide attempts.

The C-SSRS collects binary responses to 11 categories: five subtypes of suicidal ideation, five subtypes of suicidal behavior, and self-injurious behavior without suicidal intent. Specifically, the following outcomes are C-SSRS categories and have binary (Yes/No) responses. The categories have been re-ordered from the actual scale to facilitate the definitions of the composite endpoints and to enable clarity in the presentation of the results.

Suicidal Ideation:

- **Category 1** - Wish to Be Dead
- **Category 2** - Non-specific Active Suicidal Thoughts
- **Category 3** - Active Suicidal Ideation with Any Methods (Not Plan) without Intent to Act
- **Category 4** - Active Suicidal Ideation with Some Intent to Act, without Specific Plan
- **Category 5** - Active Suicidal Ideation with Specific Plan and Intent

Suicidal Behavior:

- **Category 6** - Preparatory Acts or Behavior
- **Category 7** - Aborted Attempt
- **Category 8** - Interrupted Attempt
- **Category 9** - Actual Attempt (non-fatal)
- **Category 10** - Completed Suicide

Other:

- **Category 11** - Non-suicidal Self-injurious Behavior

In addition, a numerical score, the Suicidal Ideation Score, will be defined as the highest suicide ideation category (1-5) at which the patient responded "Yes" for the given visit. If the patient did not respond "Yes" to any of these categories, the score will be set to zero.

For each of the aforementioned 11 categories, the number and percent of patients with a "Yes" response at any time post-baseline (regardless of baseline response) will be summarized by dose level. Emergent suicidal ideation or behavior will be summarized.

The listed binary categories and the Suicidal Ideation Score will be used to identify a number of composite suicidal endpoints. Note that "recent history" for these composite endpoints is defined as the 12 months prior to Screening and the Screening period. At the Screening visit, CSSRS data is collected for the prior 12 months. Therefore, analyses that utilize data from "recent history" will include the historical 12-month data collected at Screening as well as all on-study C-SSRS data collected prior to first dose. The endpoints are defined as follows:

- **Suicidal Ideation:** A "Yes" answer at any time post-first-dose to any one of the five suicidal ideation questions (Categories 1-5), regardless of the pre-dose responses
- **Suicidal Behavior:** A "Yes" answer at any time post-first-dose to any one of the five suicidal behavior questions (Categories 6-10), regardless of the pre-dose responses.
- **Suicidal Ideation or Behavior:** A "Yes" answer at any time post-first-dose to any one of the ten suicidal ideation or behavior questions (Categories 1-10), regardless of the pre-dose responses.
- **Treatment-Emergent Suicidal Ideation compared to recent history:** A maximum post-first-dose suicidal ideation score that is increased from the maximum suicidal ideation score in recent history.
- **Treatment-Emergent Serious Suicidal Ideation compared to recent history:** A maximum post-first-dose suicidal ideation score of 4 or 5 when the maximum suicidal ideation score during recent history was less than 4 (i.e., scores of 0-3). Only patients with a recent history score of 0-3 will be considered evaluable for this outcome.
- **Emergence of Serious Suicidal Ideation compared to recent history:** A maximum post-first-dose suicidal ideation score of 4 or 5 when the maximum suicidal ideation score during recent history was 0. Only patients with a recent history score of 0 will be considered evaluable for this outcome.
- **Improvement in Suicidal Ideation compared to baseline:** A decrease in the suicidal ideation score at the patient's Study Day 127 (last day for the Treatment Period) C-SSRS assessment compared to the baseline score, defined as the last measurement taken prior to first dose. Only patients with a baseline score >0 will be considered evaluable for these outcomes.
- **Emergence of Suicidal Behavior compared to all prior history:** The occurrence of suicidal behavior (a "Yes" response to one or more of Categories 6-10) post-first dose from not having suicidal behavior prior to first dose (includes the "lifetime" score collected at the Screening Visit as well as all C-SSRS assessments collected from the Screening Visit through pre-dose on Study Day 1).

Each of the composite endpoints will be summarized by dose level and study day. For each treatment emergent outcome listed, only those patients with the specified screening condition will be considered evaluable. In addition, patients who discontinue from the study with no post-first dose C-SSRS assessment will be considered unevaluable for analyses of suicidality. Percentages will be based on the number of evaluable patients for each outcome.

In addition, a shift table will be created to demonstrate the change in suicidal ideation score from recent history to treatment period and/or post-treatment period. The maximum suicidal ideation score in each period will be used to create the shift table. If a patient's recent history suicidal ideation score is missing but has a post-first-dose score, then the recent history assessment will be labeled as "unknown". Likewise, if a patient's recent history suicidal ideation score is available but has no post-first-dose score, then the scores during the treatment and post-treatment period will be labeled as "unknown".

4.8 CLINICAL OUTCOMES AND PHARMACODYNAMICS

Clinical-reported outcomes and pharmacodynamic parameters considered for analysis are outlined in Section 2.3.3 and detailed information is presented in the following sub-sections. Refer to the study protocol (Appendices 3 and 4) for a summary of all clinical endpoints with respect to number of items recorded and duration.

4.8.1 Describing Parameters over Time

All clinical outcomes will only be collected at Screening and follow-up visits, hence, descriptive tables (Table 5) will be presented at these two visits (including change from baseline at follow-up visit), while association analysis (Table 6) involving these parameters will only be presented at baseline.

As presented in Table 5, for PD biomarkers, descriptive tables will be presented per each time point and dose level. Additionally, for biomarkers, spaghetti plots (with overlaid median) for absolute, change and percent change from baseline values using untransformed data will be presented for all parameters by treatment dose level. In addition, individual patient profiles for selected biomarkers on absolute, change and percent change from baseline will be presented on the same page.

4.8.1.1 Unified Huntington's Disease rating Scale

The Composite Unified Huntington's Disease Rating Scale (cUHDRS) [4] is defined as a combination of the following first 4 individual assessments:

- Total Functional Capacity**

The Total Functional Capacity (TFC) represents the Investigator's assessment of the patient's capacity to perform a wide range of activities of daily living including working, chores, managing finances, eating, dressing and bathing. The 5-item assessment is based on a brief interview with the patient and the study companion

(if available). The TFC score ranges from 0 to 13, with a higher score representing better functioning.

- **Total Motor Scale**

The Total Motor Scale (TMS) is the sum of the individual motor ratings obtained during administration of the motor assessment portion of the UHDRS by the investigator. The score ranges from 0 to 124, with a higher score representing more severe impairment.

- **Symbol Digit Modalities Test**

The Symbol Digit Modalities Test (SDMT) is used to assess attention, visuoperceptual processing, working memory and psychomotor speed. It has been shown to have strong reliability and validity [5] [6]. The patient must pair abstract symbols with specific numbers according to a translation key. The test measures the number of items correctly paired (maximum of 110) in 90 seconds.

- **Stroop Word Reading Test**

The Stroop Word Reading Test (SWRT) is a measure of processing and psychomotor speed and depends upon quick verbal motor output. Patients are presented with a page of color names (i.e., "BLUE," "RED," or "GREEN") printed in black ink and are asked to read aloud as many words as possible within a given amount of time (typically within 45 seconds). The number of words read correctly is counted and higher scores indicate better cognitive performance.

Based on the aforementioned assessments, the following formula is used to derive the cUHDRS;

$$cUHDRS = \left(\frac{TFC - 8.8}{2.8} \right) - \left(\frac{TMS - 34.4}{17.4} \right) + \left(\frac{SDMT - 25.2}{12.4} \right) + \left(\frac{SWRT - 58}{21.2} \right) + 10.0$$

- **Independence Scale**

The patient's Independence Scale (IS) is the Investigator's assessment of the patient's degree of independence and is a subscale of the UHDRS. The scale consists of 19 discrete levels ranging from 10 to 100 (by 5), in which a score of 100 indicates no special care is needed and a score of 10 indicates the patient is fed by tube and requires total bed care.

Descriptive tables will be provided as described in Section 4.8.1 and Table 5 for cUHDRS, its individual components and IS.

4.8.1.2 Huntington's Disease Daily Activities Scale

The Huntington's Disease Daily Activities Scale (HD-DAS) assesses patients' daily function. Following a semi-structured interview with the patient and/or study companion, the patient's ability to perform daily tasks such as eating or using a telephone will be recorded. Each item is scored on a 4-point Likert-type scale, where 0 indicates no impact and 3 indicates severe impact.

Descriptive tables will be provided as described in Section [4.8.1](#) and [Table 5](#).

4.8.1.3 Clinical Global Impression-Severity

The Clinical Global Impression-Severity (CGI-S) is a single-item measure of current global severity and is completed by the clinician at clinic visits. The CGI-S is assessed using an 11-point numeric rating scale, where higher scores indicate greater severity.

Descriptive tables will be provided as described in Section [4.8.1](#) and [Table 5](#).

4.8.1.4 Clinical Global Impression-Change

The Clinical Global Impression-Change (CGI-C) is a single-item measure of change in global status (since starting the study) and is completed by the clinician at the follow-up visit. The CGI-C has seven response options: *"very much worse,"* *"much worse,"* *"minimally worse,"* *"no change,"* *"minimally improved,"* *"much improved,"* and *"very much improved."* To assess the relevance of this change, a follow up question with dichotomous response options ("yes" or "no") asks if the change has had a meaningful impact on the patient's well-being.

Descriptive tables will be provided as described in Section [4.8.1](#) and [Table 5](#).

4.8.1.5 Montreal Cognitive Assessment

The Montreal Cognitive Assessment (MoCA) is a patient-completed assessment used to detect cognitive impairment. The MoCA contains a series of basic assessments, including attention and visuospatial tasks. The total score ranges from 0 to 30, where lower scores indicate greater impairment.

Descriptive tables will be provided as described in Section [4.8.1](#) and [Table 5](#).

4.8.1.6 Summary of outputs for describing the parameters over time

Table 5. Overview of planned outputs to describe parameter evolution over time

Parameter	Output Presentation		Data Type			Time points
	Plot	Table	Absolute	Change	%Change	
mHtt	Y	Y	Y	Y	Y	All available
CSF NfL	Y	Y	Y	Y	Y	All available
Plasma NfL	Y	Y	Y	Y	Y	All available
BSI (MRI)*		Y		Y	Y	BSL, FU
Baseline MRI Volume ^f		Y	Y			BSL only
PK	Y	Y	Y			All available
ADA		Y	Y			All available
UHDRS ⁺		Y	Y	Y		BSL, FU
MoCA		Y	Y	Y		BSL, FU
HD-DAS		Y	Y	Y		BSL, FU
CGI ⁺⁺		Y	Y	Y		BSL, FU

- Absolute=measured data at a given time point
- BSL=Baseline
- FU=Follow-up
- Change (%Change) = change from BSL from a given post-BSL measurement (expressed as a percentage)

+ The parameters considered are cUHDRS, its individual components as well the Independence Scale (IS)

++ The parameters considered are CGI-S and CGI-C

* BSI=Boundary Shift Integral. BSI is already a measure of change in volume (thus the change is not derived as for the other variables). More specifically, %-Change for BSI is derived as $\left(\frac{BSI}{baseline\ volume} \right) \cdot 100$

f Baseline MRI Volume will be reported as 'raw' as well as normalized by intra-cranial volume when available

4.8.2 Relationship between selected parameters

Relationship between biomarkers and between biomarkers and clinical outcomes will be assessed as outlined in [Table 6](#) (e.g. to assess the association between CSF mHtt and CSF NfL).

For CSF/plasma biomarkers (e.g. NfL, mHtt) and CSF protein, scatter plots to assess relationships will be based on the natural log-transformed parameter.

Scatter plots between selected pairs of continuous variables will be presented based on data types shown in [Table 6](#) for X (main predictor, e.g. CSF mHtt) and Y (response, e.g. CSF NfL) variables at each indicated time point separately and data points will be colored by dose level.

Due to small sample sizes involved in these data, no formal statistical modeling will be performed, spearman's correlation coefficient over all dose groups will be used to measure the strength of association between two variables. The coefficient and 95% confidence interval will be presented in/around the scatter plots.

Table 6. Overview of planned outputs to describe the association between selected pairs of parameters

Paired Variables	Data Type				Time points	
	X-variable		Y-variable			
	Absolute	Change	Absolute	Change		
X=mHtt, Y=CSF-Nfl	Y		Y		X & Y = BSL	
		Y		Y	X & Y = All available	
X=CSF-Nfl, Y=Plasma-Nfl	Y		Y		X & Y = BSL	
		Y		Y	X & Y = All available	
X=mHtt, Y=Clinical Outcomes [§]	Y		Y		X & Y = BSL	
X= CSF-Nfl, Y= Clinical Outcomes [§]	Y		Y		X & Y = BSL	
X= Plasma-Nfl, Y= Clinical Outcomes [§]	Y		Y		X & Y = BSL	
X= Baseline MRI Volume*, Y= Clinical Outcomes [§]	Y		Y		X & Y = BSL	

• BSL=Baseline

§ Clinical Outcomes will include cUHDRS, TFC, TMS, SDMT, SWRT, MoCA, HD-DAS, CGI-S and CGI-C

* For the analysis, both 'raw' and 'normalized' Baseline MRI Volume will be considered when available

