3.3 RATIONALE FOR STUDY DESIGN

3.3.1 Rationale for RO7234292 Dose and Schedule

In order to characterize the concentration time profile of RO7234292 and mHTT in plasma and CSF and the influence of dose on the magnitude and duration of mHTT lowering in CSF, initially, two IT bolus doses ranging from 30 mg up to 120 mg given 28 days apart will be investigated in the present study. Data from the completed Phase I/Ia multiple ascending dose (MAD) study (ISIS 443139-CS1) showed doses up to 120 mg IT RO7234292 over four doses administered every 28 days were safe and well tolerated. Dose-dependent reductions of CSF mHTT from baseline at the end of the dosing interval after IT administration of doses ranging from 10 mg to 120 mg were observed.

In the chronic toxicology study in monkeys, the No Observed Adverse Effect Level was determined to be 35 mg dose. Conservatively correcting for differences in CSF volume between monkeys (\leq 15 mL) and humans (\geq 150 mL) with a scaling factor of 10, the human equivalent dose corresponds to 350 mg, representing a 3-fold safety margin to the proposed maximum dose of 120 mg, to be evaluated in the present study.

Further details on non-clinical and clinical studies can be found in the Roche Investigator's Brochure.

The target reduction for clinical efficacy based on a non-clinical PK/PD model is at least 30% reduction in CSF mHTT. The administration of two IT doses of RO7234292 lead to trough percentage change of CSF mHTT of -25%, -28%, and -30% on average for 60 mg, 90 mg, and 120 mg of RO7234292 in the Phase I/Ia MAD study (ISIS 443139-CS1).

Using a model developed based on data from the completed Phase I/IIa study *and the ongoing OLE Study BN40697*, non-linear mixed-effects simulations predict *two* IT doses of 30 mg, 60 mg, 90 mg, and 120 mg of RO7234292 are to result in *median* percentage change from baseline of CSF mHTT of -24%, -27%, -29%, and -30%, respectively, *at the end of the dosing interval (29 days) after the second IT administration*. Therefore, in order to characterize a mHTT concentration-time curve in the relevant range of mHTT reduction (~30% reduction), two IT doses administered every 4 weeks will be studied in this study.

Once a clear concentration effect has been established (peak effect and time course of effect) the information may inform a different dose regimen, including the potential for less frequent dosing.

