2. STUDY DESIGN

Eligible subjects will receive dose assigned to the cohort they are allocated to. Three dose levels are tentatively planned as follows:

- Dose level 1: 120 mg RO7234292 (n=4 patients)
- Dose level 2: 60 mg RO7234292 (n=4 patients)
- Dose level 3: 30 mg RO7234292 (n=4 patients)

This is not a randomization study. Patients are allocated to a cohort and hereby dose level according to the way they are sequentially enrolled into the study. Thus, the first 4 subjects will be assigned to 120mg, the next 4 subjects to 60mg and the next 4 subjects to 90mg.

After a review of medical data from the initial 3 dose levels and initial set of patients, a decision will be made whether to enroll additional patients and, in this case, whether to repeat a dose level, or to evaluate a lower or intermediate dose levels. The final number of dose levels and total number of patients assigned to a given dose level will be defined during the study. Up to a maximum of 20 patients will be enrolled in the whole study and the highest tested RO7234292 dose in this study will not exceed 120 mg, which is the highest test dose in the previous Phase I/IIa clinical study (ISIS 443139-CS1).

Study day is calculated relative to the date of first dose administration in Study BP40410. Study Day 1 will be the first treatment dose administration date. There is no day zero, hence the study day for patients who took at least one dose will be computed as follows:

Study Day = assessment date – treatment start date + 1,

if the assessment date is on or after the treatment date; or

Study Day = assessment date – treatment start date,

if the assessment date is earlier than the treatment date.

The end of this study is defined as the date when the last patient, last visit occurs. The end of the study is expected to occur approximately 6 months after the last study drug administration for the last patient has occurred. The total length of the study, from screening of the first patient to the end of the study, is expected to be approximately 1.5 years.

After completing study treatment in the current study, the patient will be eligible to enroll in an open label extension (OLE) study (BN40955) with active RO7234292 compound, provided the data from the ongoing RO7234292 program support continued development, the patient meets the inclusion and exclusion criteria for the OLE, and the OLE meets approval by the relevant competent authorities, IRBs, and ECs.

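### The change-from-baseline correlations in SAP Table 6 are pooled over dose, so they mix any shared dose shift with within-dose association; a dose-adjusted coefficient should sit beside them.

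*SAP*

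**What the plan says.** SAP 4.8.2 sets out scatter plots for the pairs in Table 6, drawn for the "variables at each indicated time point separately and data points will be colored by dose level". The summary of each plot is a Spearman coefficient: "correlation coefficient over all dose groups will be used to measure the strength of association between two variables". It adds that "The coefficient and 95% confidence interval will be presented in/around the scatter plots", without naming a CI method. Because the sample is small, "no formal statistical modeling will be performed".

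Two pairs have a change-versus-change row at all available time points: "X=mHtt, Y=CSF-Nfl", and CSF NfL with plasma NfL. Every other row of Table 6 is baseline only.

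On dose, SAP Section 2 lists 120, 60 and 30 mg with four patients each and states: "Patients are allocated to a cohort and hereby dose level according to the way they are sequentially enrolled into the study". Protocol 3.3.1 reports from the earlier study "Dose-dependent reductions of CSF mHTT from baseline at the end of the dosing interval after IT administration" and gives model predictions by dose. Neither document gives a dose response for NfL.

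**The concern.** Dose can act as a common cause of both changes. If it moves each marker, patients on different doses separate along both axes, and the pooled coefficient departs from zero even when the markers are unrelated among patients on the same dose. Colouring the points shows the clustering but alters neither the coefficient nor its CI. No partial or within-dose coefficient is planned. The mixed-effects work in SAP 4.9 covers drug concentrations, mHTT and exposure-response, not the association of one biomarker with another.

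Dose level also follows enrolment order, so anything that changed during the study is aliased with it. One candidate is catheter time. Protocol 5.1.1.4 refers to six patients in this study whose catheter stayed in for 4 days, whereas the current protocol removes it at 48 hours. If those six were the first enrolled (an inference), they are all four 120 mg patients and two at 60 mg. The documents do not show that this affects NfL.

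Relationships between biomarkers are a stated exploratory objective. A reader given only the pooled coefficient cannot tell a dose shift from a patient-level link.

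**Working it through.** The plan states no expected correlation or precision for Table 6, so there is no figure to reproduce.

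**Inputs from the documents**
- Three dose levels with four patients each, n = 12 (SAP Section 2). The list there gives 30 mg as the third level, while the sentence after it sends the third group of four to 90 mg. The two must be reconciled, because the dose spread depends on them. The listed levels, which agree with Protocol 3.1, are used here.
- Predicted median mHTT change at 30, 60 and 120 mg: -24%, -27% and -30%, at the end of the dosing interval after the second dose (Protocol 3.3.1).

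**Assumptions**
- The within-dose SD of mHTT change and any NfL dose response are not given, so ranges are used.
- Change is taken on the natural-log scale that SAP 4.8.2 specifies for these plots. Its ranks are then those of percentage change.
- Errors are normal and independent within dose, so the true within-dose association is zero.

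**Approximate size.** With equal group sizes and the same standardised response in both markers:

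induced correlation = between-dose variance / (between-dose variance + within-dose variance)

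Between-dose variance of (-24, -27, -30) = (9 + 0 + 9)/3 = 6. This gives:
- SD 3: 6/(6 + 9) = 0.40
- SD 5: 6/(6 + 25) = 0.19
- SD 10: 6/(6 + 100) = 0.057
- SD 15: 6/(6 + 225) = 0.026

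**Simulation.** 40,000 trials per setting, Fisher-z intervals with SE 1/√(n-3) for the pooled coefficient. The adjusted coefficient uses ranks centred within dose level, with SE 1/√(n-2-3).

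| Assumed SD (points) | Mean pooled rho | Pooled CI excludes 0 | Mean adjusted rho | Adjusted CI excludes 0 |
|---|---|---|---|---|
| 3 | 0.42 | 28% | 0.00 | 5.5% |
| 5 | 0.19 | 9.5% | 0.00 | 5.2% |
| 10 | 0.05 to 0.06 | 5.5% | 0.00 | 5.2% |
| 15 | 0.03 | 5.2% | 0.00 | 5.2% |

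The 1.06 factor often used in the SE for Spearman lowers the 28% to about 25%.

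**Other settings**
- mHTT SD 10 with a stronger NfL response, 1 or 2 SD per dose level: pooled rho 0.15 or 0.21; CI excludes zero in 8% or 10%.
- Only one marker responds to dose: pooled rho 0.00; CI excludes zero in 5%.
- Markers move in opposite directions, 1 SD per level: pooled rho -0.42. With a true within-dose correlation of 0.6, the pooled mean is -0.13 and the adjusted mean 0.50, so pooling can also hide a real link.

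**Precision at r = 0**
- Pooled half-width: tanh(1.96/√9) = 0.57.
- Adjusted half-width: tanh(1.96/√7) = 0.63.

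**The case against.** The strongest reply has four parts.

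1. **The premise is half supported.** Both markers must shift with dose, and only mHTT is shown to do so. For CSF NfL with plasma NfL, neither marker has a documented dose response. The mHTT evidence also concerns the end of the dosing interval, whereas Table 6 includes CSF samples from 4 to 48 hours after the first dose. This stands, and it makes the point conditional.

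2. **Large artefacts need small SDs.** The predicted steps are 3 points per dose level, so steps of 0.5, 1.0 and 1.5 SD require SDs of 6, 3 and 2 points. A reader might infer from such scenarios that the planned coefficients will be seriously spurious. The documents do not support that: at an SD of 10 points the artefact is about a tenth of the CI half-width.

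3. **The pooled coefficient is a legitimate summary.** The SAP says openly that it spans all dose groups and does not claim a within-dose link. If dose moves one marker through the other, the between-dose variation is signal. With a within-dose correlation of 0.5, all of the dose effect mediated and 1 SD per level, the pooled CI excludes zero in 48% of trials and the adjusted CI in 24% (SE with the 1.06 factor). This stands. It rules out the tempting step of replacing the pooled value or resting conclusions on the adjusted one alone.

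4. **Readers have other information.** By-dose tables and plots of each marker are planned (SAP 4.8.1 and Table 5). They would reveal a shared shift, but they do not quantify the association that remains once it is removed.

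**Conclusion.** The point holds in a conditional form. The Change rows carry a single coefficient that cannot separate between-dose shift from within-dose association. The distortion is non-zero only if both markers move with dose or with something aliased with it, and its sign depends on whether they move in the same direction.

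Under the protocol's predicted mHTT means and an assumed equal NfL response, it runs from about 0.42 (SD 3 points) through 0.19 (SD 5) to between 0.05 and 0.06 (SD 10), against a half-width of about 0.57. The SD and the NfL response are assumptions, so the actual size cannot be fixed from the documents.

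The baseline rows precede dosing and are unaffected. No primary or secondary endpoint, dose decision or safety conclusion is shown to depend on these coefficients. This is a cheap improvement to an exploratory output.

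**What to change.** In SAP 4.8.2, for the Change rows of Table 6 only:
- Report a dose-adjusted Spearman coefficient beside the pooled one. Centre the ranks of each variable within dose level, correlate the centred ranks, and base the CI on the reduced degrees of freedom (two fewer with three dose levels). Name the CI method for both coefficients.
- Label the pooled coefficient as including between-dose differences, and do not describe it alone as a within-dose, patient-level link.
- Keep the pooled coefficient, and do not make the adjusted one the sole basis for conclusions. Leave the baseline rows as they are.

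The cost is a sentence or two in the SAP and one more coefficient per plot. It needs no formal model and no separate correlations within groups of four. The adjusted interval is wider (0.63 against 0.57 at zero), and the adjusted value is less sensitive when one marker truly mediates the dose effect on the other.
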